APPENDIX V - NCI COMMON TERMINOLOGY CRITERIA FOR ADVERSE EVENTS

The descriptions and grading scales found in the NCI Common Terminology Criteria for Adverse Events (CTCAE) version 4.0 will be utilized for Adverse Event (AE) reporting. All appropriate treatment areas should have access to a copy of the CTCAE version 4.0. A copy of the CTCAE version 4.0 can be downloaded from the CTEP web site

(http://ctep.cancer.gov/protocolDevelopment/electronic_applications/ctc.htm).

Please note:

HEMATOLOGICAL AND PSYCHIATRIC TOXICITY SHOULD BE GRADED ACCORDING TO CRITERIA DESCRIBED IN SECTION 8.3.

APPENDIX VI - CLL DIAGNOSTIC CRITERIA AND INDICATIONS FOR TREATMENT
(Abbreviated from the 2008 International Workshop on Chronic Lymphocytic Leukemia Guidelines)

Diagnosis

- a. Presence of at least 5×10^9 B lymphocytes /L (5000/ μ L) in the peripheral blood, of which prolymphocytes comprise no more than 55%.
- b. Monoclonal B-cells (either kappa or lambda light chain restricted) that are clonally co-expressing at least one B-cell marker (CD19, CD20, or CD23) and CD5.

Indications for treatment

- a. Evidence of progressive marrow failure as manifested by the development of, or worsening of, anemia or thrombocytopenia.
- b. Massive (i.e. at least 6 cm below the left costal margin), progressive, or symptomatic splenomegaly.
- c. Massive nodes (i.e. At least 10 cm in longest diameter), progressive, or symptomatic lymphadenopathy.
- d. Progressive lymphocytosis with an increase of more than 50% over a 2-month period or lymphocyte doubling time (LDT) of less than 6 months (which may be extrapolated). Lymphocyte doubling time can be obtained by linear regression extrapolation of absolute lymphocyte counts obtained at intervals of 2 weeks over an observation period of 2 to 3 months. In patients with initial blood lymphocyte counts of less than 30×10^9 /L (30,000/ μ L), LDT should not be used as a single parameter to define indication for treatment.
- e. Constitutional symptoms, defined as 1 or more of the following disease-related symptoms or signs:
 - Unintentional weight loss of 10% or more within the previous 6 months prior to screening
 - Significant fatigue (inability to work or perform usual activities)
 - Fevers higher than 100.5°F or 38.0°C for 2 or more weeks without evidence of infection or
 - Night sweats for more than 1 month without evidence of infection.

APPENDIX VII - CYP3A INHIBITORS/INDUCERS AND CYP450 SUBSTRATES

Table 1. List of prohibited CYP3A inhibitors and inducers

Strong CYP3A inhibitors	Strong CYP3A inducers
boceprevir	avasimibe
clarithromycin*	carbamazepine *
conivaptan	fosphenytoin *
elvitegravir	phenobarbital *
indinavir	phenytoin *
itraconazole	primidone *
ketoconazole	rifabutin
lopinavir*	rifampin
mibefradil	St. John's Wort
nefazodone	
nelfinavir	
posaconazole	
ritonavir*	
saquinavir*	
telaprevir	
telithromycin	
tipranavir	
troleandomycin	
voriconazole	

* These drugs are Enzyme Inducing Anti-Epileptic drugs
This database of CYP inhibitors and inducers was compiled from the Indiana University School of Medicine's "Clinically Relevant" Table, from the University of Washington's Drug Interaction Database based on in vitro studies and from the FDA's "Guidance for Industry, Drug Interaction Studies;" from the Indiana University School of Medicine's "Clinically Relevant" Table.

Table 2. List of CYP450 substrates to be used with caution

CYP2C8	CYP2C9	CYP2C19	CYP3A*	
amodiaquine	celecoxib	amitriptyline	adinazolam	felodipine ¹
cerivastatin	diclofenac	citalopram	alfentanil ^{1,2}	fentanyl ²
pioglitazone	flurbiprofen	clobazam	alpha-dihydroergocryptine ¹	flunitrazepam
repaglinide	fluvastatin	clomipramine	alprazolam	fluticasone ¹
rosiglitazone	glibenclamide (glyburide)	clopidogrel	amlodipine	lovastatin ¹
torasemide	gliclazide	diazepam	aripiprazole	maraviroc ¹
troglitazone	glimepiride	fluoxetine	atorvastatin	midazolam ¹
	glipizide	imipramine	brecanavir	nifedipine
	indomethacin	lansoprazole	brotizolam ¹	nisoldipine
	irbesartan	mephobarbital	budesonide ¹	nitrendipine
	ketobemidone	moclobemide	buspirone ¹	perospirone ¹
	lornoxicam	omeprazole	capravirine	quinine
	losartan	pantoprazole	cerivastatin	sildenafil ¹
	meloxicam	progesterone	chlorpheniramine	simvastatin ¹
	naproxen	quazepam	cyclosporine ²	sirolimus ^{1,2}
	nateglinide	rabeprazole	darifenacin ¹	tolvaptan
	piroxicam	sertraline	diazepam	trazodone
	rosiglitazone	S-mephenytoin	diergotamine ²	triazolam ¹
	S-ibuprofen		ebastine ¹	
	sulfamethoxazole		eletriptan ¹	
	tenoxicam		eplerenone ¹	
	tolbutamide		ergotamine ²	
	torasemide		estazolam	
	valdecoxib		everolimus ¹	

* CYP3A substrates were compiled from the Indiana University School of Medicine's "Clinically Relevant" Table; and supplemented by the FDA's "Guidance for Industry, Drug Interaction Studies" and the University of Washington's Drug Interaction Database.

1 Sensitive substrates: Drugs whose plasma AUC values have been shown to increase 5-fold or higher when co-administered with a strong inhibitor of the respective enzyme.

2 Substrates with narrow therapeutic index (NTI): Drugs whose exposure-response indicates that increases in their exposure levels by the concomitant use of strong inhibitors may lead to serious safety concerns (e.g., Torsades de Pointes).

AMEND #1: 2015-OCT-22

APPENDIX VIII - QT PROLONGING DRUGS

Updates to this list will be published on the trial website.

List of prohibited QT prolonging drugs with known risk of Torsades de Pointes

Drug	QT risk(*)	Comment
Amiodarone	Known risk for TdP	Females>Males, TdP risk regarded as low
Arsenic trioxide	Known risk for TdP	
Astemizole	Known risk for TdP	No Longer available in U.S.
Bepridil	Known risk for TdP	Females>Males
Chloroquine	Known risk for TdP	
Chlorpromazine	Known risk for TdP	
Cisapride	Known risk for TdP	Restricted availability; Females>Males.
Disopyramide	Known risk for TdP	Females>Males
Dofetilide	Known risk for TdP	
Domperidone	Known risk for TdP	Not available in the U.S.
Droperidol	Known risk for TdP	
Halofantrine	Known risk for TdP	Females>Males
Haloperidol	Known risk for TdP	When given intravenously or at higher-than- recommended doses, risk of sudden death, QT prolongation and torsades increases.
Ibutilide	Known risk for TdP	Females>Males
Levomethadyl	Known risk for TdP	
Mesoridazine	Known risk for TdP	
Methadone	Known risk for TdP	Females>Males
Pentamidine	Known risk for TdP	Females>Males
Pimozide	Known risk for TdP	Females>Males
Probuconol	Known risk for TdP	No longer available in U.S.
Procainamide	Known risk for TdP	
Quetiapine	Possible risk for TdP	Prohibited as this drug is a sensitive 3A4 substrate
Quinidine	Known risk for TdP	Females>Males
Sotalol	Known risk for TdP	Females>Males
Sparfloxacin	Known risk for TdP	
Tacrolimus	Possible risk for TdP	Prohibited as this drug is a sensitive 3A4 substrate with narrow TI
Terfenadine	Known risk for TdP	No longer available in U.S.
Thioridazine	Known risk for TdP	
Vardenafil	Possible risk for TdP	Prohibited as this drug is a sensitive 3A4 substrate
(*) Classification according to the Qtcdrugs.org Advisory Board of the Arizona CERT Sensitive substrates: Drugs whose plasma AUC values have been shown to increase 5-fold or higher when co-administered with a potent inhibitor of the respective enzyme.		
Note: drugs with a known risk for TdP that are also strong inhibitors of CYP3A are not repeated here and only mentioned in Table 1.		

List of QT prolonging drugs to be used with caution

Updates to this list will be published on the trial website.

Drug	QT risk (*)
Alfuzosin	Possible risk for TdP
Amantadine	Possible risk for TdP
Amitriptyline	Conditional risk for TdP
Azithromycin	Possible risk for TdP
Chloral hydrate	Possible risk for TdP
Citalopram	Conditional risk for TdP
Clomipramine	Conditional risk for TdP

Statistical analysis plan for I216

June 28, 2017

By [name]

The analysis will be descriptive with continuous variable measured by mean and SD or median and range and categorical variable measured by percentage.

Table 1 to table 12 are the same as the meeting book table and no additional program is needed.

Table 13: Duration of response. Median (Min, Max) of the duration of the response will be reported for patients with CR/CRu and PR.

Response duration will be measured from the time measurement criteria for CR/PR (whichever is first recorded) are first met until the first date that recurrent or progressive disease is objectively documented, taking as reference the smallest measurements recorded on study (including baseline).

Figure 1. Waterfall plot for tumour shrinkage

Figure 2. KM plot for PFS

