9.3 Evaluation After Protocol Treatment

All patients will be seen 4 weeks after the end of the last cycle (4 Week Post Treatment Report).

Patients whose treatment is permanently discontinued due to an adverse event or non-hepatic clinically significant laboratory value, should be followed as clinically indicated until resolved to \leq grade 2. See Section 8.4.3 for more detailed guidance on patients who discontinue study treatment due to hepatic toxicity.

Follow-up beyond the 4 week treatment report is not required for patients who go off protocol treatment with progressive disease, except to document ongoing toxicities (until resolved to \leq grade 2), late toxicities (including second malignancies) and death if within 30 days of last dose.

For patients who go off protocol treatment with objective CR, PR or SD ongoing, follow up including response assessment will be required every three months until relapse/progression (Follow-Up Report). If the patient starts new anticancer therapy, contact the study coordinator to discuss whether further follow-up is required.

For patients who go off protocol therapy with suspected PR or CR, an 8 week confirmatory response assessment including CT scanning will be required as per Sections 9.1 and 10.4, if not already performed.

A Death Report is only required if death occurs within 30 days of last dose or if patient dies before progression/relapse; due within 2 weeks of knowledge of death (see Appendix IV –Documentation for Study).

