10.5 Response Duration

Response duration will be measured from the time measurement criteria for CR/PR (whichever is first recorded) are first met until the first date that recurrent or progressive disease is objectively documented, taking as reference the smallest measurements recorded on study (including baseline).

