10.7 Progression-Free Survival

Progression-free survival (PFS) is defined as the time from study entry until disease progression or death.

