12.2 Duration of Protocol Treatment

(see Section 10.0 for response definition)

- For patients who achieve a complete or partial response, therapy will continue until objective disease progression or unacceptable toxicity, whichever occurs first.
- For stable patients, therapy will continue for a maximum of 6 cycles (24 weeks). Patients who have no evidence of tumour shrinkage at this point should go off therapy and receive other treatment at the investigator's discretion.
- Patients who progress (treatment failure) will go off study at the time progression is documented clinically and/or radiographically.

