RELAPSE/PROGRESSION REPORT	To be completed at the time of disease relapse or progression. Due within 2 weeks after contact with patient.	Relevant radiology reports.

continued on next page ...

Form	To be Completed/Submitted Electronically:	Supporting Documentation to be sent using Supporting Document Upload Tool
DEATH REPORT	Required only on patients who die during protocol therapy, within 30 days after last dose, or within the protocol defined follow-up period for patients with response or stable disease ongoing.* Due within 2 weeks of knowledge of death.	Autopsy report, if done.
SERIOUS ADVERSE EVENT REPORT FORM	All reportable serious adverse events must be reported as described in Section 11.0. All reportable serious adverse events must be reported as described in Section 11.0. Preliminary CCTG Serious Adverse Event Report due within 24 hours. Updated CCTG Serious Adverse Event Report due within 7 days .	
* NB It is the investigator's responsibility to investigate and report the date/cause of death of any patient who dies during this period. Any death that occurs during this period and that is thought to be treatment related must also be reported as a Serious Adverse Event as described in Section 11.		

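### SAP Table 13 summarises duration of response as a median and range, with no rule for responses that have no documented progression at the analysis

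*SAP*

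**What the plan says.** The SAP's general rule is: "The analysis will be descriptive with continuous variable measured by mean and SD or median and range". Table 13 then specifies: "Median (Min, Max) of the duration of the response will be reported for patients with CR/CRu and PR". Its only Kaplan-Meier output is "Figure 2. KM plot for PFS".

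The SAP repeats the definition in Protocol 10.5: duration runs from first meeting the CR or PR criteria "until the first date that recurrent or progressive disease is objectively documented". Death is not an end point of that interval. It is for PFS (Protocol 10.7): "Progression-free survival (PFS) is defined as the time from study entry until disease progression or death".

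Duration of response is a named secondary endpoint (Protocol 1.2.2 and 14.1). On follow-up:

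- Protocol 12.2: for responders, "therapy will continue until objective disease progression or unacceptable toxicity, whichever occurs first".
- Protocol 14.2: accrual of up to 29 patients over 24 months, then six months of follow-up after the last enrolment. No data cut is fixed.
- Protocol 9.3: responders who are off treatment are assessed every three months until relapse or progression. Once new anticancer therapy starts, further follow-up is settled case by case.
- Deaths in response are expected on the forms. Protocol 9.3 asks for a Death Report "if patient dies before progression/relapse", and Appendix IV asks for one for deaths "within the protocol defined follow-up period for patients with response or stable disease ongoing".

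**The concern.** Duration of response is a time-to-event quantity, but Table 13 treats it like any other continuous variable. A responder with no documented progression has no end date under 10.5, so someone must decide at the analysis whether to use the time observed so far, drop the patient, or censor. The documents do not make that choice, and the options give different medians from the same data.

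The first two options tend to shorten the median when durations are long relative to follow-up. Counting the response as complete treats the time so far as the whole duration. Leaving it out removes mainly the longer responses. The reported maximum may also be a response that has not ended. A reader of the table could not tell which durations are finished, and this is a named secondary efficacy endpoint.

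**Working it through.** **1. Is a rule given anywhere?** No. Protocol 10.5 and the SAP give the start and end of the interval only. Protocol 10.7 defines PFS without a censoring rule that could be borrowed. The protocol's own Kaplan-Meier text (14.5) concerns the survival scale. SAP Tables 1 to 12 refer to a meeting book that is not among the documents, but Table 13 is specified in the SAP itself.

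**2. Can the case arise?** Yes, in two ways. A patient can still be in response at the analysis (12.2, 14.2, 9.3), or can die in response (9.3, Appendix IV).

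**3. How many responders?** At the 30% alternative, 12 × 0.30 = 3.6. Under the two-stage rule of 14.2 (stop at 0 of 5):

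- P(0 or 1 responder) = 0.70^5 + 5 × 0.30 × 0.70^4 × 0.70^7 = 0.168 + 0.030 = 0.198.
- Expected responders = 5 × 0.30 + (1 − 0.168) × 7 × 0.30 = 3.247. Given at least 2: (3.247 − 0.030) / 0.802 = 4.0.

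Four responders are used below.

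**4. Share of responses ongoing.** The documents give no expected duration and no data cut, so there is no figure to reproduce and everything from here is assumed. Entry is uniform over 24 months. This is the accrual period of 14.2, which is stated for up to 29 patients; applying it to the 12-patient cohort alone is an assumption. Response occurs 8 weeks (1.84 months) after entry. Duration is the 8-week minimum of 10.4 plus an exponential time with rate λ = ln 2 / (m − 1.84), where m is the true median. For a cut at month C:

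P(ongoing) = [exp(−λa) − exp(−λb)] / (24λ), with a = C − 24 − 3.68 and b = C − 3.68.

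For C = 30 and m = 12: λ = 0.0682, a = 2.32, b = 26.32, so (0.854 − 0.166) / 1.637 = 0.420. At least one of four ongoing: 1 − 0.580^4 = 0.89.

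**5. Effect on the summary.** Simulation with 100,000 trials per setting, 4 responders and a cut at month 30. Typical means the median over simulated trials, in months. The Kaplan-Meier median is taken at the midpoint when S(t) equals 0.5.

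| Assumed true median | 6 | 12 | 24 |
|---|---|---|---|
| Responses ongoing | 17% | 42% | 65% |
| At least one of 4 ongoing | 52% | 89% | 99% |
| Typical median, full follow-up | 6.3 | 12.7 | 25.5 |
| Ongoing counted as complete | 5.8 | 9.1 | 12.1 |
| Ongoing left out | 5.3 | 7.4 | 8.7 |
| Kaplan-Meier, not reached ranked as long | 6.3 | 12.1 | 22.6 |
| Kaplan-Meier median not reached | 1% | 16% | 47% |
| Maximum is an ongoing response | 28% | 61% | 82% |

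**6. Sensitivity.**

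- Cut at month 36: 6% / 28% / 54% ongoing; counted as complete 6.3 / 11.4 / 15.9; left out about 5.9 / 8.7 / 10.5. With a true median of 6, counting ongoing responses as complete costs nothing.
- Seven responders (12 × 0.30 + 17 × 0.20 = 7.0, with the exploratory cohort full at its illustrative 20%), month 30: full follow-up 6.0 / 12.0 / 24.0; counted as complete 5.6 / 8.8 / 11.8; left out 5.2 / 7.2 / 8.6.

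**7. Small invented example.** Durations 3, 6+, 9 and 14+ months, with + for ongoing. All counted as complete: (6 + 9) / 2 = 7.5. Ongoing left out: (3 + 9) / 2 = 6.0. Kaplan-Meier: S = 3/4 after month 3 and 3/4 × 1/2 = 3/8 at month 9, so the median is 9.0.

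**The case against.** The strongest reply is that this hardly matters here. The SAP is openly descriptive and the primary test does not use duration. At the 5% null rate the two-stage rule gives 0 or 1 responder with probability 0.95^5 + 5 × 0.05 × 0.95^4 × 0.95^7 = 0.774 + 0.142 = 0.916, so the table may be nearly empty. With 4 responders noise exceeds the bias: with full follow-up and a true median of 12, the 5th to 95th percentile range of the sample median is about 5.2 to 27.7 months. Six months is required follow-up and not a data cut, and 9.3 follows off-treatment responders to relapse or progression, so a later analysis would shrink the effect. All of this stands. It limits the size of the point, but the table would still not show which durations are unfinished.

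Three stronger readings are tempting, and the documents do not support them:

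- A reader might infer that the SAP prescribes an ordinary median. It names no estimator, and its wording does not exclude a Kaplan-Meier median. An ordinary median is the natural reading; what is established is the missing rule.
- A reader might infer that Kaplan-Meier would be about as biased with 4 responders. That impression comes from looking only at trials in which the median is reached. At a true median of 24 those give about 14.6, because the 47% of trials in which it is not reached are dropped. Ranking those trials as long gives about 22.6. The fair statement is that the median is imprecise, and that a summary restricted to trials where it is reached would be too low.
- A reader might infer that CRu in Table 13 is a slip for CRi. Protocol 10.4 has no CRu, but it defines both CRi and nodular PR, and nothing says which categories were meant. That is a query to the sponsor.

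**Conclusion.** The point holds as a reporting and estimation gap in a secondary, descriptive endpoint. Table 13 applies a median and range to a duration that may have no end date, and neither document says how such a response is handled. Ongoing responses and deaths in response are both foreseeable from the protocol.

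The direction is clear: counting unfinished responses as complete, or leaving them out, tends to shorten the median when durations are long relative to follow-up. The size rests wholly on the assumed durations, accrual pattern and cut. At month 30 it runs from about half a month to one month at a true median of 6, up to more than half of the median at 24. If every response has ended in documented progression by the analysis, there is no bias. Nothing here bears on the response-rate test in 14.2.

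**What to change.** In SAP Table 13:

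- List each responder's duration, with a plus sign where no progression is documented. Give the number still responding, and mark the range in the same way. This works with any number of responders and is the main change.
- State that responses without documented progression are censored at the last disease assessment. Report a Kaplan-Meier median with its confidence interval, or say that it was not reached. State the median convention, for example the midpoint when S(t) equals 0.5.
- Keep the event definition of Protocol 10.5 and report deaths without progression separately. Note that censoring these deaths may be informative and may lengthen the median. A sensitivity summary counting death as an event can be made from the same data.
- Ask the sponsor which response categories CRu is meant to cover.

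The cost is a few SAP sentences. The dates come from the Treatment, Follow-up, Relapse/Progression and Death Reports of Appendix IV, and a Kaplan-Meier program is already needed for Figure 2. The protocol need not change. The downside is that with few responders the median may not be reached or its interval may be very wide, and the caveat on censored deaths remains.
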